In a separate study, we found that fluoroquinolones are frequently prescribed for extended surgical prophylaxis in patients undergoing urologic procedures.¹⁶ The frequent use of fluoroquinolones is concerning given the strong association between fluoroquinolone use and several adverse events, including CDI.¹⁷

In December 2018, our study team surveyed 110 hospitals within the research network of the Society for Healthcare Epidemiology of America. Forty hospitals (36.4%) responded. Among the 38 hospitals that performed urologic procedures, 18 (47.4%) had never audited whether urologists at their facility adhered to the AUA guidelines for post-procedural antimicrobial use. In the hospitals that did audit, 30% reported that antimicrobials were always prescribed for more than 24 hours. Another 30% reported prolonged post-procedural courses were prescribed in some patients.

These findings suggest that there is an unrecognized opportunity to evaluate and potentially improve antimicrobial-prescribing in patients undergoing urologic procedures. The following study will leverage audit-and-feedback plus additional implementation strategies with the goal of reducing unnecessary post-procedural antimicrobial use after 3 common urologic procedures. The findings from this pilot trial could inform a larger intervention across the VHA to reduce the use of excessive post-procedural antimicrobial prophylaxis in urologic patients.

METHODS

Trial design:

We will use a before/after quasi-experimental design, which will be analyzed with an interrupted time-series analysis.

Participants:

Eligibility criteria: There will be 3 intervention VHA hospitals. To be eligible, a VHA hospital must perform the following 3 urologic procedures: transurethral resection of the prostate (TURP), transurethral resection of a bladder tumor (TUBRT), and ureteroscopy (URS). Eligible VAMCs needed to perform these three index procedures, perform at least 75 qualifying procedures per year, and utilize excess post-procedural antimicrobial in the highest tertile for all sites.

Method of recruitment: The Chief of Urology at an eligible intervention sites will be contacted by e-mail. A follow-up Microsoft Teams or Zoom call will be scheduled to explain the project, if the Chief of Urology is interested in potentially participating.

Interventions:

- Content: Feedback on the percentage of patients who underwent a qualifying procedure and received an antimicrobial on post-procedural day 1

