- Delivery method: At baseline, feedback will be given via a video-conferencing call in which we show the team their feedback report and explain what it means. All subsequent feedback will be delivered through e-mail.
- Unit of delivery: The feedback will be given to all practicing urologists at a site.
- Deliverer: The baseline video-conferencing call will be attended by the study team (Drs. [name], [name] and [name]). The electronic feedback will be sent from the PI's e-mail account.
- Setting: The intervention will be delivered via video-conferencing (baseline) or via e-mail (months 1, 3, 5, 7, 9, and 11).
- Exposure quantity and duration: Feedback will be given at baseline and every 2 months
- Time span: 12 months
- Activities to increase compliance or adherence: During the introductory call, the study team will review the AUA's guidelines on antimicrobial prophylaxis and the potential harms of extending antimicrobial prophylaxis beyond a single dose.^{15,18} The Chief of Urology at each site will be encouraged to be a local champion for more judicious use of post-procedural antibiotics.

Objectives:

- Study objectives: Evaluate whether a pilot audit-and-feedback intervention across 3 hospitals can safely reduce the unnecessary use of post-procedural antimicrobials in patients undergoing urologic procedures.
- Hypotheses: An bundled intervention across 3 hospitals will facilitate safe reductions in post-procedural antimicrobial-prescribing.

Outcomes:

Clinical outcomes are listed below. Data for all clinical outcomes will be extracted from the Corporate Data Warehouse (CDW) using the VA Informatics and Computing Infrastructure (VINCI).

Primary outcome

Excess post-procedural antimicrobial use is defined as a prescription for a designated antimicrobial agent on post-procedural day one. Designated antimicrobials will be antimicrobial agents potentially used for a urinary tract-related indication, as outlined in our prior work.⁵ This definition will be used to minimize the chance of including patients receiving antimicrobials for non-urologic or non-prophylactic indications.

Patients will be eligible for this outcome if they underwent a medical procedure coded with a Current Procedural Terminology (CPT) code or an International Classification of Diseases, 10th version, Procedure Coding System (ICD-10-PCS) code for TURPs, TURBTs, and URSs during

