the 2-year baseline period or during the 1-year intervention period. These three procedures were selected because they are all common procedures performed endoscopically with no skin incision required. In addition, for all 3 procedures, the AUA guidelines give a clear recommendation for giving a single dose of antimicrobial prophylaxis.¹⁵

Secondary outcomes

Excess post-procedural antimicrobial duration is defined as the duration of continuous excessive post-procedural antimicrobial use, as quantified as days of therapy per National Healthcare Safety Network methodology.¹⁹

Safety outcomes

- Late antimicrobial prescription is defined as the prescription of a designated antimicrobial that does not qualify as a post-procedural antimicrobial (see above) by any provider within 7-30 days of the date of the patient's urologic procedure. All late antimicrobial prescriptions must be agents potentially used for a urinary tract-related indication, as outlined in our prior work.⁵
- Return visits: seeking care in an Emergency Department, Urgent Care Clinic or hospital readmission to an acute-care bed at a VHA facility for any indication within 30 days of the patient's index urologic procedure.

Assignment Method: Intervention sites will be selected from the top tertile of all sites, as ranked on the frequency of excess post-procedural antimicrobial-prescribing. Eligible new sites will be invited until 3 unique sites agree to participate.

Sample Size: This was a pilot trial, so no sample size calculation was performed.

Blinding: None

Unit of Analysis: Each medical center (3 intervention)

Statistical Methods:

Patient demographics, comorbidities, and types of procedures are presented by count and percentages. Observations occurring within the implementation phase (July 2022) were omitted from all analyses. Observations from each of the three sites were stratified into three data sets to accommodate separate analyses on each site.

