To model the primary outcome, we used a logistic regression model and a set of three explanatory variables: time, a binary indicator for an observation occurring within the intervention phase, and an interaction term between these two main effects (time and intervention). Time was measured in days divided by 365, giving an annualized figure for the time coefficient estimate and interaction coefficient. In the tables of results of these logistic regression models, the coefficient estimates are exponentiated to display estimated multiplicative effect on the odds; 95% confidence intervals are also provided on the odds scale. The median duration of post-procedural antimicrobial prescriptions at each site were compared using the Wilcoxon rank-sum test.

To model the secondary outcomes, we used a similar approach to what is described above with the addition of a fourth explanatory variable (a binary indicator for the primary outcome) to the

logistic regression model. This last variables was included to assess the risk of these secondary outcomes in patients who were not exposed to post-procedural antimicrobials compared to those who were exposed.

References:

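### Sites are selected for a high rate of the primary outcome and the ranking period is not stated, so regression to the mean can bias the before/after estimate if that period overlaps the baseline.

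*Combined protocol and SAP*

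**What the plan says.** Selection appears twice. Eligibility criteria require a site to "perform at least 75 qualifying procedures per year, and utilize excess post-procedural antimicrobial in the highest tertile for all sites". Assignment Method repeats the rule: "Intervention sites will be selected from the top tertile of all sites, as ranked on the frequency of excess post-procedural antimicrobial-prescribing".

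The primary outcome carries the same name: "Excess post-procedural antimicrobial use is defined as a prescription for a designated antimicrobial agent on post-procedural day one". The plan gives no separate definition for the ranking measure. The outcome is collected over "the 2-year baseline period or during the 1-year intervention period".

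Trial design reads: "We will use a before/after quasi-experimental design, which will be analyzed with an interrupted time-series analysis". Only intervention sites are included, and under Statistical Methods "Observations from each of the three sites were stratified into three data sets to accommodate separate analyses on each site". The primary model is a logistic regression on "time, a binary indicator for an observation occurring within the intervention phase, and an interaction term between these two main effects (time and intervention".

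The plan does not say which months were used for ranking, whether they lie inside the baseline, or how regression to the mean is to be handled.

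**The concern.** A site enters because its observed rate was high when it was ranked. Part of a high observed rate is chance, or a temporary swing in practice, and that part tends to fall back with no feedback at all. If the ranking months are also baseline months, the comparator is inflated by selection.

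An interrupted time series protects against a stable earlier trend, but not against this. If the last baseline year was the ranking year, that year is selectively high, the fitted slope tilts upward, and the projected no-intervention rate is too high.

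The same rule applies at all three sites, so any such bias has the same expected direction at each. A fall seen at every site would not rule it out. The pilot is meant to inform a larger programme, so a biased estimate could carry forward.

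**Working it through.** The plan has no sample size or power figure to reproduce. The check is how large a spurious change the selection rule can produce when feedback has no effect.

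**Inputs from the document.** At least 75 procedures a year (Eligibility criteria); hospital-level median 27.9%, IQR 14.7-55.0%, for bladder tumour resection only (Background); two baseline years and one intervention year (Primary outcome). **Assumed.** 90 hospitals, all at the stated volume; independent yearly practice deviations with SD 0, 0.3 or 0.5 logits.

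**Step 1: excess in the ranking year from sampling noise.** Between-site SD = (55.0 - 14.7)/1.349 = 29.9 points. Sampling SD at 75 procedures = sqrt(0.279 × 0.721/75) = 5.2 points, or sqrt(0.55 × 0.45/75) = 5.7 points. Reliability = 1 - (sampling SD/29.9)² = 0.97 to 0.96. The mean z of the top third is 1.091, so the expected excess is d = (1 - reliability) × 1.091 × 29.9 = 1.0 to 1.2 points. At 150 procedures it is 0.5 to 0.6.

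**Step 2: what a straight-line segmented fit does with that excess.** Centre the two baseline years at zero, so time runs from -1 to +1 with variance 1/3. The 6-month point of the intervention year is then at 1.5.
- Last year high by d: fitted mean d/2, slope (d/4)/(1/3) = 0.75d, projection d/2 + 1.5 × 0.75d = 1.625d. Spurious change -1.625d.
- Both years high by d₂: spurious change -d₂. From sampling noise, d₂ is about half of d.
- First year high by d: projection d/2 - 1.125d = -0.625d. Spurious change +0.625d.
- Ranking before the baseline: no excess in the baseline, change 0.

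With d near 1.0 these are -1.6, -0.5, +0.6 and 0 points.

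**Step 3: simulation with no intervention effect.** Hospital logits are normal with mean logit(0.279) and SD (0.201 + 1.758)/1.349 = 1.45. The top third is selected and the segmented line is fitted to its mean rates. Change at 6 months, in percentage points, at 75 procedures a year:

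| Ranking window | Sampling noise only | SD 0.3 to 0.5 logits (assumed) |
|---|---|---|
| Last baseline year | -1.6 | about -4 to -8 |
| Both baseline years | -0.5 | about -1.2 to -2.6 |
| First baseline year | +0.6 | about +1.6 to +3.3 |
| Before the baseline | 0 | about 0 |

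Cross-check: for SD 0.5 ranked on the last year, the simulated rates were 58.8%, 63.6% and 58.6%. So d = 63.6 - 58.7 = 4.9, and 1.625 × 4.9 = 8.0. At 150 procedures a year the sampling-noise column is about halved.

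**Step 4: the planned model.** A separate simulation fitted the per-site logistic model, with a different rate distribution, 100 sites, 75 or 150 procedures a year, and slowly drifting practice with SD 0 to 0.6 logits (all assumed). The null 6-month odds ratio was 0.80-0.98 when ranked on the last 12 months, 0.93-1.00 on both years, and 1.02-1.11 before the baseline. The first-year window was not run in this model.

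**Step 5: precision at one site.** At a 60% rate and 75 procedures a year, the approximate 95% half-width is 1.96 × sqrt(0.24 × [1/n + D²/(nV) + 1/75]). Here n is baseline procedures, D the distance in years from the baseline centre to the 6-month point, and V the variance of baseline time.
- Plan: n = 150, D = 1.5, V = 1/3. Half-width about 24 points.
- Last year removed, two earlier years used: D = 2.5. About 36 points, 1.5-fold.
- Last year removed, three earlier years: n = 225, D = 3, V = 0.75. About 25 points.
- Both years removed, two earlier years: n = 150, D = 3.5, V = 1/3. About 2-fold.
- Last year removed, no extension: n = 75, D = 2, V = 1/12. About 3.2-fold.

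**The case against.** Overlap is not shown. The plan is silent on the ranking period, and silence is not evidence that ranking used baseline data. If ranking used earlier data, the threat to the segmented model largely disappears. Nor is the sign fixed: first-year ranking biases against the intervention. On the document's own figures, sampling noise gives at most about 1.6 points against a half-width of about 24 points at one site. That is minor for a three-site pilot, and 75 is a minimum volume. The larger figures need a yearly variation that the document does not give. They also need deviations that change exactly at the year boundaries, which maximises the tilt.

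All of that stands, and it limits the size and direction of the point. It does not remove the point, because the plan gives the reader no means of telling which row of the table applies.

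Two stronger readings are tempting. One is that the bias necessarily favours the intervention; the document does not support this, since the sign depends on a period it does not state. The other is that selection makes false-positive results common. In the drift simulation at SD 0.6, ranking on the last 12 months gave a falsely significant 6-month reduction in 15.0% (75 a year) or 21.9% (150 a year) of site fits. Choosing sites on their true rate already gave 9.2% and 15.4%. Most of that excess comes from treating procedures as independent, which is a separate matter.

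**Conclusion.** The point holds conditionally. Sites are selected on the construct that is the primary outcome, nothing separates ranking months from baseline months, and neither comparison sites nor the three-term model would correct an overlap. The size runs from nothing to about 1.6 points on sampling noise. It could reach about 8 points in the intervention's favour only with last-year ranking and assumed practice variation of 0.5 logits.

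A reader might infer that regression to the mean would account for any fall that the trial reports. The figures do not support that: this mechanism alone could not explain a large fall. The estimates also rest on a spread from one procedure type that itself contains sampling error, and on an assumed number of hospitals, volumes and practice variation. The change is worth making because it is cheap and stating one fact may settle the matter.

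**What to change.** 1. State the ranking period and whether it overlaps the 2-year baseline. If it lies wholly before the baseline, say so; no refit is needed.
2. If it overlaps, extend the Corporate Data Warehouse extract back and refit each site's primary model without the ranking months, as a sensitivity analysis. The protocol is dated March 2024 and its methods are partly in the past tense, with July 2022 already omitted as the implementation month. Label the refit post hoc where data are already in hand.
3. Show each site's day-1 rate before, during and after the ranking window.
4. Report both estimates with intervals. If they differ materially, state that regression to the mean cannot be excluded. Do not adopt the smaller estimate by rule: taking the minimum of two noisy estimates biases toward no effect.

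Cost: a longer extract, one refit per site, and an older baseline extrapolated across the removed months. When one year is removed, about three non-ranking years keep precision close to the plan's, and only two widen intervals about 1.5-fold. When both baseline years are removed, two earlier years widen them about 2-fold. Removing the last year without extending the extract is not worthwhile, at about 3.2-fold.

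### The primary per-site logistic model neither checks nor allows for month-to-month extra variation or serial correlation; if either is present, its 95% intervals will be too narrow

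*Combined protocol and SAP*

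**What the plan says.** The Trial design section describes a before/after quasi-experimental design, "which will be analyzed with an interrupted time-series analysis". Under Outcomes, eligible procedures are those in "the 2-year baseline period or during the 1-year intervention period". The Statistical Methods omit July 2022 as the implementation phase and fit each site alone: "Observations from each of the three sites were stratified into three data sets to accommodate separate analyses on each site".

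The model itself is short: "To model the primary outcome, we used a logistic regression model and a set of three explanatory variables". The three variables are time, a phase indicator and "an interaction term between these two main effects (time and intervention". The time scale ("Time was measured in days divided by 365") shows that the rows are individual procedures rather than monthly totals. On precision, the plan says only that "95% confidence intervals are also provided on the odds scale".

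The documents name no month effect, dispersion parameter, autocorrelation term, robust variance or residual check.

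**The concern.** An ordinary logistic regression takes its standard errors from the binomial variance alone. That is right if, given the fitted line, two procedures in the same month at the same hospital are no more alike than two procedures a year apart. It is not right if a hospital's prescribing moves up or down as a whole for a month or more. The design itself expects collective movement: feedback goes to all practicing urologists at a site, and the Chief of Urology is encouraged to act as a local champion. Ordinary drift of this kind, unrelated to the intervention, would then be counted as many independent observations when it is really one shared shift.

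What is at stake is the stated uncertainty of the main result. There is no control site, so each site's interval is the main guard against reading drift as an intervention effect. The protocol says the pilot could inform a larger VHA intervention. The concern is with the intervals, not with the point estimates.

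**Working it through.** The plan states no interval, power or sample size, so there is no figure to reproduce. The check asks how the planned model behaves when there is no true effect.

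**Inputs from the documents**
- Series: 24 baseline months and 12 intervention months, with one month omitted between them.
- Volume: at least 75 qualifying procedures a year (Eligibility criteria), i.e. 75/12 = 6.25 a month.
- Base rate: 55%. This is the upper quartile of hospitals for bladder tumor resection in the Background, used here as an assumption for a top-tertile site. The national 37.2% served as a check.

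**Assumptions not in the documents**
- Month-level SD *s* on the logit of 0, 0.3 or 0.5. At 50% use, one SD either side is 43-57% for 0.3 and 38-62% for 0.5.
- Lag-1 correlation ρ of 0 or 0.5.
- Volumes of 150 and 300 a year.
- Ordinary model-based standard errors, because the plan names no other kind.

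**Hand check, ρ = 0.** With *m* procedures in an average month, Poisson counts and use *p*, the variance is inflated by about 1 + *m s*² *p*(1−*p*). Here *p*(1−*p*) = 0.55 × 0.45 = 0.2475.
- 75 a year, *s* = 0.3: 1 + 6.25 × 0.09 × 0.2475 = 1.139. The SE ratio is √1.139 = 1.067, and the non-coverage is 2[1 − Φ(1.96/1.067)] = 6.6%.
- 150 a year, *s* = 0.5: 1 + 12.5 × 0.25 × 0.2475 = 1.773. The SE ratio is √1.773 = 1.332, and the non-coverage is 2[1 − Φ(1.96/1.332)] = 14.1%.

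The inflation grows with monthly volume, so busier sites are affected more.

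**Simulation** of the plan's three-term model at one site, 2,000 runs per cell. Each cell gives non-coverage of the nominal 95% interval (phase / interaction, %), then the ratio of true to model SE for the phase term.

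| s, ρ | 75/yr | 150/yr | 300/yr |
|---|---|---|---|
| 0, 0 | 5.1 / 4.6; 1.01 | 5.3 / 5.7; 1.02 | 4.9 / 5.0; 1.01 |
| 0.3, 0 | 7.2 / 5.9; 1.08 | 7.1 / 8.3; 1.13 | 11.0 / 11.0; 1.25 |
| 0.3, 0.5 | 7.5 / 7.8; 1.14 | 12.3 / 13.7; 1.30 | 16.8 / 18.0; 1.44 |
| 0.5, 0 | 9.3 / 10.0; 1.19 | 13.6 / 14.0; 1.34 | 20.5 / 19.2; 1.55 |
| 0.5, 0.5 | 12.7 / 12.6; 1.33 | 18.8 / 22.2; 1.54 | 34.1 / 32.8; 2.06 |

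The first row shows that the simulation is calibrated, and the ρ = 0 rows agree with the hand check. At a base rate of 37.2% and 150 a year the picture is the same: 5.9 / 5.7 with no extra variation, 12.3 / 11.1 for (0.3, 0.5) and 19.3 / 20.8 for (0.5, 0.5). Taking simulation error and repeat runs together, the ranges with extra variation are about 5-13% at 75 a year and 7-23% at 150 a year.

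**Stable differences between urologists.** With five urologists, a between-urologist SD of 1 or 2, 150 procedures a year and an unchanged roster, coverage stayed at 94.3-95.5%. That source alone does not create the problem.

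**Behaviour of a simple repair.** Scaling the standard errors by the square root of the monthly Pearson dispersion (never below 1), with t intervals on 36 − 4 = 32 df, gives error of about 3-4% with no extra variation and about the nominal 5% with extra variation but ρ = 0. With ρ = 0.5 the error is about 6-18%, so the repair is then only partial.

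**The case against.** The best counter-argument is that the documents show neither extra variation nor serial correlation. They contain no monthly series, no dispersion estimate and no interval. A reader might infer that the trial's reported intervals are in fact too narrow. The documents do not support that: with no extra variation the planned intervals are correct. The wide spread between hospitals in the Background suggests that prescribing is a local habit, but it says nothing about movement from month to month within a hospital. This objection stands, and the point has to be conditional.

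Other parts also stand:
- The only volume the documents give is the 75-a-year floor, where small uncorrelated variation costs little (7.2 / 5.9%). The largest figures need an assumed 300 a year.
- Sites come from the top tertile, so use may be well above 55%, which shrinks the effect. At an assumed 80% use with SD 0.3 and correlation 0.5, the error is 6.8% at 75 a year and 9% at 150.
- The standard-error method is unstated, so a robust variance is not strictly excluded, although model-based errors are the natural reading.
- The plan sets no significance level or decision rule. The error rates above only restate interval coverage.

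A reader might also see a contradiction between the per-procedure model and "Unit of Analysis: Each medical center (3 intervention". There is none that matters here, since that line fits three separate site analyses.

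The pilot label does not remove the point. The plan still reports 95% intervals as its statement of uncertainty, and a larger study may lean on them.

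**Conclusion.** The point holds in conditional form. The plan specifies an ordinary logistic regression of single procedures for what it calls an interrupted time series, and it neither checks nor allows for overdispersion by month or serial correlation. If either is present, the intervals for the phase and interaction odds ratios will be too narrow, with error of about 5-13% at 75 procedures a year and about 7-23% at an assumed 150 a year, against a nominal 5%. These figures rest on the assumed SD of 0.3-0.5 and lag-1 correlation of 0-0.5, and on model-based standard errors. The direction does not depend on the exact values.

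For a pilot with no formal decision rule this is an improvement that should be made, not a flaw that invalidates the analysis.

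**What to change.** Keep the three terms and the separate site fits, and add the following to the Statistical Methods.

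1. State how the standard errors are computed.
2. For each site, group procedures by calendar month and report the Pearson dispersion and the residual lag-1 correlation. Both would also help in planning a larger VHA study.
3. Multiply the standard errors by the square root of the dispersion, never below 1, and use t-based intervals on about 32 df.
4. Report beside these the intervals from a model with an autocorrelated month-level effect. Rely on those if residual autocorrelation is evident, because dispersion scaling only partly corrects for it.

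The logistic models for the other outcomes follow a similar approach, so the same check is worth running there.

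The cost is a few sentences and a few lines of code, using procedure dates and outcomes that the analysis already needs. The downside is somewhat wider intervals, slightly conservative (about 3-4% error) if there is no extra variation. With about 6 procedures a month at the volume floor, the autocorrelation will be poorly estimated, which is a reason to show both sets of intervals.

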The Surgical Care Improvement Project (SCIP) also used audit-and-feedback to improve antimicrobial-prescribing among surgical inpatients. SCIP was a nationwide initiative to reduce surgical complications through accountability and public disclosure. Ambulatory surgeries and urologic procedures were not included in SCIP. Compliance with SCIP standard 3, the discontinuation of antimicrobials within 24 hours of the operation, increased from <60% at baseline to 94% in 2012.¹³ These improvements were achieved even before CMS tied SCIP measures to hospital reimbursements in fiscal year 2013.

Although audit-and-feedback has been effective in improving antimicrobial-prescribing among certain types of surgical specialties, its benefit among urologic providers is unclear. In 2015, urologists accounted for the 8th highest number of outpatient antimicrobial prescriptions among all specialties.¹⁴ Given such a high frequency of antimicrobial-prescribing, there may be opportunities for enhanced antimicrobial stewardship among urologists.

The Best Practice Policy Statement on Urologic Surgery Antimicrobial Prophylaxis, published by the American Urological Association (AUA), recommends single-dose antimicrobial prophylaxis without post-procedural continuation is recommended for most urologic procedures.¹⁵

However, the unnecessary use of post-procedural antimicrobials is common after urologic procedures, according to administrative data our group analyzed from the VHA. In a national

cohort of nearly 30,000 patients, extended post-procedural antimicrobials (defined as >24 hours) were prescribed after 37.2% of urologic procedures for a median duration of 3.0 excess days.⁵ Based on a manual chart validation, 177 of 211 (83.9%) patients who received excessive post-procedural antimicrobials (i.e. more than 24 hours after the procedure) did not have a clear indication for antimicrobial therapy. At the hospital-level, the use of excessive post-procedural antimicrobials varied widely. For example, after transurethral resection of bladder tumors, the median frequency of excessive post-procedural antimicrobial-prescribing at the hospital-level was 27.9% with an interquartile range of 14.7-55.0%. Overall, we estimate that there are 30,000 days of unnecessary antimicrobial therapy per year in VHA patients undergoing these three urologic procedures.

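### No model includes procedure type: if prescribing differs by procedure and the mix departs from its baseline trend, a site's phase or interaction odds ratio is biased; the safety models' exposure term is also unadjusted for procedure

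*Combined protocol and SAP*

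**What the plan says.** All of this is in the combined protocol and SAP.

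- **Primary model (Statistical Methods).** "we used a logistic regression model and a set of three explanatory variables". The three are time in years, an intervention-phase indicator and their product.
- **Per-site analysis (same section).** "Observations from each of the three sites were stratified into three data sets to accommodate separate analyses on each site". The Trial design section describes a before/after design, and the only units are three intervention hospitals, so there is no control series.
- **Procedure type (same section).** "Patient demographics, comorbidities, and types of procedures are presented by count and percentages". This is its only stated use. No adjustment, stratification, standardisation or sensitivity analysis by procedure is described.
- **Later models (same section).** They follow the same approach "with the addition of a fourth explanatory variable (a binary indicator for the primary outcome"), whose purpose is to "assess the risk of these secondary outcomes in patients who were not exposed to post-procedural antimicrobials compared to those who were exposed". I take these to be the models for late prescriptions and return visits. The plan lists those two as safety outcomes, but they are the only other binary ones: the listed secondary outcome is a duration, and durations are compared by a rank-sum test.
- **Objective (Objectives).** To evaluate whether the intervention "can safely reduce the unnecessary use of post-procedural antimicrobials in patients undergoing urologic procedures".

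**The concern.** The primary outcome pools three procedures. A segmented model protects against a smooth trend in the pooled rate. It does not protect against a change in composition that starts at or after the interruption. Two conditions must hold together for bias: prescribing differs by procedure within the site, and the mix leaves its baseline trend. An abrupt change then loads on the phase term, and a change that grows through the intervention year loads on the interaction. Fitting sites separately removes mix differences between sites but not a change within one.

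The exposure term needs no mix change. It is a non-randomised comparison of patients with no patient or procedure covariate. If procedure type predicts both antimicrobial exposure and the later event, the OR is confounded in either direction. Upward bias would make withholding antimicrobials look safer than it is, which bears on the safety half of the objective.

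**Working it through.** The plan states no figure on this point, so there is none to reproduce. All mixes, rates and risks below are assumptions, and no true effect is present.

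**Inputs from the document.** Two baseline years and one intervention year; July 2022 omitted (31 days); at least 75 procedures a year (Eligibility criteria), so 150 + 75 = 225 at the minimum.

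**Assumed inputs.** Baseline mix TURBT/TURP/ureteroscopy 30/30/40%. Prescribing 40/55/70% (30-point gap) or 45/52.5/60% (15-point gap). Uniform dates. Time zero at the intervention start, which the plan does not specify; the interaction does not depend on it, but the phase coefficient does.

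**1. Abrupt shift from ureteroscopy to TURBT.** Pooled baseline rate with the 30-point gap: 0.3×0.40 + 0.3×0.55 + 0.4×0.70 = 0.565. With the 15-point gap: 0.5325. Each shift lowers the pooled rate by shift × gap.

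| Gap | Shift | Pooled rate | Null phase OR |
|---|---|---|---|
| 30 points | 10 | 0.565 to 0.535 | 0.89 |
| 30 points | 20 | 0.565 to 0.505 | 0.79 |
| 15 points | 10 | 0.5325 to 0.5175 | 0.94 |
| 15 points | 20 | 0.5325 to 0.5025 | 0.89 |

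Check by approximation: bias in log OR ≈ shift × gap / [p(1−p)] = 0.20 × 0.30 / 0.2475 = 0.242, OR 0.785.

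**2. Other patterns.** A 20-point shift that grows over the intervention year leaves the phase OR near 1.00 and moves the interaction OR to about 0.79 (30-point gap) or 0.89 (15-point gap). A steady linear drift over all three years is absorbed by time: both ORs are 1.00. Equal rates across procedures give no bias whatever the mix.

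**3. Against sampling error at 75 a year.**
- Phase: baseline part (1/150)(1 + 1.085²/(1/3)) = 0.0302; intervention part 4/75 = 0.0533; SE = √(0.0835/0.2475) = 0.58.
- Interaction: 1/(150 × 1/3) + 1/(75 × 1/12) = 0.02 + 0.16; SE = √(0.18/0.2475) = 0.85.
- Largest bias above: 0.242/0.58 = 0.42 SE (phase) and 0.242/0.85 = 0.28 SE (interaction).
- The simulated false-positive rate for the 20-point abrupt shift at 75 a year is 7.0% (30-point gap) or 5.6% (15-point gap). At an assumed 300 a year it is 12.9% or 6.6%.
- With a 40% ureteroscopy share and the 30-point gap, even moving all 40 points takes the pooled rate from 0.565 to 0.445: OR 0.62, log 0.48, or 0.48/0.58 = 0.83 SE. One SE therefore cannot be reached at 75 a year by this move. At 300 a year the SE is 0.29, and one SE needs 0.29 × 0.2475/0.30 = 0.24, a 24-point shift.

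**4. Exposure term, no true effect.** Event risks 8/10/12% (TURBT/TURP/ureteroscopy), 30-point gap: exposed 0.0597/0.565 = 10.57%, unexposed 0.0423/0.435 = 9.72%, OR 1.10. With the 15-point gap: 10.39% against 9.98%, OR 1.05. The more extreme values, 1.26 and 0.85, need the wide gap and event risks of 5/10/15% or 16/12/8%. The SE at 225 procedures is 0.42 to 0.45, so even 1.26 (log 0.23) is about 0.5 SE.

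**5. What procedure type cannot remove.** The Background chart validation reports that "177 of 211 (83.9%) patients who received excessive post-procedural antimicrobials" had no clear indication, which leaves 34 of 211 (16.1%). If that share carried over, no unexposed patient had an indication, and those patients had 1.5, 2 or 3 times an assumed 10% event risk, the exposed risk is 10% × (0.839 + 0.161 × ratio) = 10.8, 11.6 or 13.2%. The null OR is then 1.09, 1.18 or 1.37, even within procedure.

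**6. With two procedure indicators added.** Phase and interaction ORs return to 1.00 in the large-sample fits, and the SE rises by about 1 to 5%.

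**The case against.** The case for leaving the plan alone is substantial.

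- **Nothing is shown at these sites.** This stands. A reader might set the overall 37.2% beside the statement that "the median frequency of excessive post-procedural antimicrobial-prescribing at the hospital-level was 27.9" per cent after TURBT and infer a difference by procedure. The first is a rate over all procedures and the second a median of hospital rates, so together they do not establish one.
- **The bias is small beside the noise.** This stands at 75 a year. At that volume chance alone moves a 40% share by ±1.96 × √[0.24 × (1/75 + 1/150)] = ±14 points between phases, which the SE already reflects. At 300 a year the figure is ±7, so a 20-point shift would mean a real service change. However, 75 is an eligibility floor, and sampling error shrinks with volume while this bias does not.
- **The pooling is reasoned.** The plan chose three endoscopic procedures with the same single-dose recommendation and feeds back one pooled percentage. That justifies a pooled outcome but does not show equal prescribing.
- **Singling out procedure type is a preference.** Partly so, since demographics and comorbidities are also unadjusted. But patients qualify through a procedure code, so the variable exists for all of them and defines the pooled denominator.
- **Adjustment leaves the larger exposure problem.** This stands: step 5 can exceed step 4. The interpretive caveat matters more there than the extra covariates.

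**Conclusion.** The omission is certain from the text; its consequence is conditional. The phase or interaction OR is biased only if prescribing differs by procedure within a site and the mix also leaves its baseline trend at or after the start. The exposure OR is confounded by procedure only if procedure type predicts both exposure and outcome, and on the reading that these models serve the binary safety outcomes.

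Under the assumptions above, the primary bias at the minimum volume is about 0.4 SE or less for shifts up to 20 points, and the procedure-driven exposure OR is 1.05 to 1.10 under mild risks. The actual size at these sites cannot be determined from the documents. A reader might infer that a reduction found under this plan would be an artefact of case mix, or that the pilot is invalid. The documents support neither, because they give no mix by period and no comparable rates by procedure. It would also be wrong to infer that procedure adjustment makes the exposure OR causal. This is a low-priority, low-cost sensitivity analysis.

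**What to change.** - **Primary model.** At each site, refit with two procedure-type indicators and a stated rule for patients with two index procedures on one day. Report the phase and interaction ORs beside those of the stated model, not in place of them. The methods are written in the past tense, so label the refit as added if the data have already been analysed.
- **Description.** Show procedure mix by phase for each site.
- **Safety models.** Refit in the same way, using Firth penalised likelihood for all of these adjusted fits rather than choosing it case by case.
- **Interpretation.** State that the exposure OR is not a causal estimate, because confounding by indication remains after procedure adjustment.

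**Cost.** Two degrees of freedom per model, an SE increase of about 1 to 5%, and a re-run on a variable already extracted. The adjusted OR is conditional on procedure type, so a small difference from the stated OR is not by itself evidence of confounding. Sparse safety events are the main burden: in simulations at 225 procedures and an assumed 5% event rate (11 to 12 events), ordinary maximum likelihood failed in 15 to 26% of fits with seven coefficients, against 5 to 6% with the present five. Penalised fits failed in at most 0.4%.
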